### 5.3.3.3 Imaging Exclusion Criteria

23. Mixed aortic valve disease (aortic stenosis and aortic regurgitation with predominant aortic regurgitation 3-4+).
24. Aortic valve is a congenital unicuspid or congenital bicuspid valve or is non-calcified as verified by echocardiography.
25. Severe ventricular dysfunction with LVEF <25% as measured by resting echocardiogram.
26. Pre-existing prosthetic heart valve or other implant in any valve position, prosthetic ring, severe circumferential mitral annular calcification (MAC) which is continuous with calcium in the left ventricular outflow tract (LVOT), severe (greater than or equal to 3+) mitral insufficiency, or severe mitral stenosis with pulmonary compromise.
27. Echocardiographic or multi-slice computed tomography (MSCT) evidence of intracardiac mass, thrombus or vegetation.
28. Significant aortic disease, including abdominal aortic or thoracic aneurysm defined as maximal luminal diameter 5cm or greater; marked tortuosity (hyperacute bend), aortic arch atheroma (especially if thick [ $> 5$  mm], protruding or ulcerated) or narrowing (especially with calcification and surface irregularities) of the abdominal or thoracic aorta, severe “unfolding” and tortuosity of the thoracic aorta (applicable for transfemoral access only)
29. Native aortic annulus size < 19 mm or > 27 mm per the baseline diagnostic imaging.
30. Aortic root angulation > 70°
31. Undue risk of coronary obstruction (e.g., bulky aortic valve leaflets in close proximity to coronary ostia)
32. Non-calcified aortic annulus
33. Iliofemoral vessel characteristics that would preclude safe insertion of the FlexNav™ Delivery System with or without an arterial introducer sheath such as severe obstructive calcification, protruding thrombus or severe tortuosity (applicable for transfemoral access only)
34. Severe tricuspid regurgitation or severe right ventricle dysfunction
35. Minimum access vessel diameter of <5.0mm for small FlexNav™ Delivery System and <5.5 mm for large FlexNav™ Delivery System
36. Ascending aorta anatomy that would preclude safe delivery of the valve to the native aortic annulus
37. Sinus of Valsalva anatomy that would prevent adequate coronary perfusion
38. Annulus eccentricity ratio <0.73

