## Clinical Investigation Plan

A larger size valve (Navitor Titan) is being added to the Navitor product line to provide a treatment option for patients with larger annulus diameters (27-30mm). Collectively, these design modifications are intended to improve clinical outcomes and ease of use for the Navitor TAVI system.

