## Clinical Investigation Plan

In case the subject does not meet all inclusion criteria or meets any of the exclusion criteria, the subject is considered a screen failure. The Principal Investigator or the delegated clinical study personnel will record the screen failure in the hospital records and on a screening log as required. Patients meeting general inclusion criteria and no exclusion criteria will be asked to sign an Informed Consent form if they wish to participate in the clinical study. These patients will also be entered into the screening log.

Upon initial screening of eligibility of patients by the heart team, subject case reviews will be conducted by an independent SSC to confirm a patient's eligibility to receive a Navitor Valve via transfemoral or alternate access implantation (specified per the IFU). The SSC will also provide final determination of a subject's risk classification for the study. If a site disagrees with the committee's final decision regarding risk classification the subject will not be eligible for implantation with the Navitor Valve and will be exited from the study as a screen failure. If the SSC does not approve the subject for study participation, the subject will be exited from the study as a screen failure and will not be counted toward the sample size of 169 analysis subjects in the Portico NG cohort or 60 analysis subjects for the Titan cohort.

Subject data will be collected following enrollment into the clinical study.

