## 5.3 Eligibility Criteria

### 5.3.1 General Eligibility Criteria

Assessment for general eligibility criteria is based on medical records of the site and interview with a candidate patient. If some of the clinical and laboratory tests are not included in site standard tests, they must be done but after written informed consent is obtained. Patients must meet ALL of the inclusion criteria to be considered for the clinical study. If ANY of the exclusion criteria are met, the patient is excluded from the clinical study and cannot be enrolled.

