#### 5.3.2.2 Imaging Inclusion Criteria

1. Subject has senile degenerative aortic valve stenosis with echo-derived criteria, defined as: aortic valve area (AVA) of  $\leq 1.0 \text{ cm}^2$  (or indexed EOA  $\leq 0.6 \text{ cm}^2/\text{m}^2$ ) AND mean gradient  $\geq 40 \text{ mmHg}$  or peak jet velocity  $\geq 4.0 \text{ m/s}$  or doppler velocity index (DVI)  $\leq 0.25$ . (Qualifying AVA baseline measurement must be within 90 days prior to informed consent).
2. Portico NG cohort (only): aortic annulus diameter of 19-27mm and ascending aorta diameter of 26-42 mm for the specified valve size listed in the IFU, as measured by CT conducted within 12 months prior to informed consent. (If a CT is contraindicated and/or not possible to be obtained for certain subjects, a 3D echocardiogram and non-contrast CT of chest and abdomen/pelvis may be accepted).

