## Clinical Investigation Plan

3. Titan cohort (only): aortic annulus diameter of 27-30 mm and ascending aorta diameter of 27-44 mm per the IFU, as measured by CT conducted within 12 months prior to informed consent. (If a CT is contraindicated and/or not possible to be obtained for certain subjects, a 3D echocardiogram and non-contrast CT of chest and abdomen/pelvis may be accepted).

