#### 10.10.1 Subject Selection Committee

The Subject Selection Committee (SSC) will consist of cardiac surgeons and cardiac interventionalists who will be responsible for ensuring subject eligibility in the clinical study according to the CIP. After Informed Consent is obtained and study eligibility is confirmed by the local heart team, subject data will be reviewed by the SSC to confirm anatomic suitability for the Navitor implant procedure based on echocardiographic and pre-implant CT measurements and appropriate risk classification of the patient as defined in the SSC Charter.

The Committee's decision on whether to include the subject in the study must be documented and communicated to the enrolling investigational site by the Sponsor. If the SSC considers the subject ineligible for participation in the study, the subject will be exited from the study and the reason for exclusion will be documented in the reviewers' feedback form. If a site disagrees with the Committee's final decision regarding risk classification the subject will not be eligible for a Navitor implant attempt in the study.

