## Clinical Investigation Plan

	
 
2. Subject has symptomatic aortic stenosis as demonstrated by NYHA Functional Classification of II, III, or IV.
 
3. Subject has senile degenerative aortic valve stenosis with echo-derived criteria, defined as: aortic valve area (AVA) of <math>\leq 1.0 \text{ cm}^2</math> (or indexed EOA <math>\leq 0.6 \text{ cm}^2/\text{m}^2</math>) AND mean gradient <math>\geq 40 \text{ mmHg}</math> or peak jet velocity <math>\geq 4.0 \text{ m/s}</math> or doppler velocity index (DVI) <math>\leq 0.25</math>. (Qualifying AVA baseline measurement must be within 90 days prior to informed consent).
 
4. Portico NG cohort (only): aortic annulus diameter of 19-27mm and ascending aorta diameter of 26-42 mm for the specified valve size listed in the IFU, as measured by CT conducted within 12 months prior to informed consent. (If a CT is contraindicated and/or not possible to be obtained for certain subjects, a 3D echocardiogram and non-contrast CT of chest and abdomen/pelvis may be accepted).
 
5. Titan cohort (only): aortic annulus diameter of 27-30mm and ascending aorta diameter of 27-44mm per the IFU, as measured by CT conducted within 12 months prior to informed consent. (If a CT is contraindicated and/or not possible to be obtained for certain subjects, a 3D echocardiogram and non-contrast CT of chest and abdomen/pelvis may be accepted).
 

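### Exclusion criterion 29 (annulus above 27 mm) carries no cohort label and contradicts the Titan inclusion range of 27–30 mm

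*Protocol*

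**What the plan says.** The annulus inclusion criteria in protocol Section 5.3.2.2 are labelled by cohort:

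- "Portico NG cohort (only): aortic annulus diameter of 19-27mm and ascending aorta diameter of 26-42 mm"
- "Titan cohort (only): aortic annulus diameter of 27-30 mm and ascending aorta diameter of 27-44 mm per the IFU"

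The CIP Summary (Appendix XXI) repeats the Titan range. Sections 1.1.1 and 15.5 both describe the Titan valve as meant for annuli of 27–30 mm.

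Exclusion criterion 29 in Section 5.3.3.3 reads "Native aortic annulus size < 19 mm or > 27 mm per the baseline diagnostic imaging". It names no cohort, and nothing in Section 5.3.3 confines the exclusion list to one cohort.

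The consequence of meeting an exclusion is stated twice. Section 5.3.1: "If ANY of the exclusion criteria are met, the patient is excluded from the clinical study and cannot be enrolled". Section 5.2.1: "In case the subject does not meet all inclusion criteria or meets any of the exclusion criteria, the subject is considered a screen failure". Section 5.4 treats such subjects as screen failures as well. Section 10.7 permits deviations only in medical emergencies, requires every deviation to be reported, and rules out waivers.

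**The concern.** The exclusion limit at the top of the Portico NG range is the bottom of the Titan range. With no cohort label on criterion 29, a patient whose annulus suits the Titan valve and exceeds 27 mm satisfies the Titan inclusion criterion and also meets an exclusion.

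A site that follows the text must screen-fail the patient. A site that follows the evident intent enrols the patient against a written exclusion and has a reportable eligibility deviation. Under Section 10.7, repeated non-compliance can end an investigator's participation.

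There is also a regulatory side. Section 3 justifies combining Titan data from a separate regional protocol partly on the ground that the two protocols have aligned eligibility criteria. That statement is harder to rely on when the criteria in this protocol contradict each other for the cohort in question.

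**Working it through.** The plan gives no figure to reproduce. The check is an intersection of intervals, followed by a search for any text that removes the conflict.

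**Inputs** (*d* = annulus diameter in mm)

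| Rule | Source | Set of *d* |
|---|---|---|
| Portico NG inclusion | Protocol 5.3.2.2 | 19 ≤ *d* ≤ 27 |
| Titan inclusion | Protocol 5.3.2.2, Appendix XXI | 27 ≤ *d* ≤ 30 |
| Not excluded by criterion 29 | Protocol 5.3.3.3 | 19 ≤ *d* ≤ 27 |

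**Eligible set = inclusion ∩ not excluded**

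- Portico NG: [19, 27] ∩ [19, 27] = [19, 27]. There is no conflict.
- Titan: [27, 30] ∩ [19, 27] = {27}. Only the single value 27 mm survives out of a range 30 − 27 = 3 mm wide. Every candidate with 27 < *d* ≤ 30 meets criterion 29.

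This assumes that one measurement serves both rules. The inclusion criterion specifies CT, while criterion 29 refers more generally to baseline imaging. Section 5.2.1 names CT as the screening method for annulus sizing, so the assumption is reasonable.

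**Does any text exempt Titan subjects?**

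- *Implied scope.* The exclusion list states scope where scope is meant. Criteria 28 and 33 are limited to transfemoral access, and criterion 35 is split by delivery-system size. Criterion 29 has no such qualifier.
- *Subject Selection Committee.* Section 10.10.1 describes its members as those "who will be responsible for ensuring subject eligibility in the clinical study according to the CIP". Section 3.2.3 has the committee apply the protocol together with the sizing advice in the instructions for use. Neither section lets it set aside a protocol exclusion.
- *CIP Summary.* It gives the Titan range and leaves the annulus limit out of its key exclusions, but it sends the reader to Section 5.3.3 for the complete list, where the conflict sits.
- *SAP.* It contains no eligibility criterion that resolves the point.

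**How many subjects**

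- Titan analysis cohort (Section 3): 60.
- US minimum: 50% × 60 = 30.
- All 60 enrolled under this protocol: up to 60 affected.
- Non-US half taken from the separate regional protocol: 60 − 30 = 30 affected.

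Both counts assume that every Titan subject measures above 27 mm. Roll-ins are outside the 60. Section 5.4.1 allows up to 20 across both cohorts, and criterion 29 would apply to any Titan roll-in too.

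**Effect on the analysis**

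Protocol Section 8.1 and SAP Section 2.1.1 define the analysis population by implant attempt, not by eligibility. A Titan subject enrolled despite criterion 29 and taken to an implant attempt is still analysed. The Titan success rule in Section 8.11 (three or fewer deaths in 60) does not change.

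**The case against.** The strongest reply is that nobody will be misled. The protocol states the Titan range consistently in four places. The CT core laboratory measures every candidate, and a central committee reviews eligibility and valve size before implant. Criterion 29 looks like Portico NG text carried forward when the Titan cohort was added. Section 5.4 shows what may be the same incomplete updating: it counts only 169 analysis subjects where Section 5.2.1 gives both 169 and 60. On this view the defect is a missing label that moves no estimate, error rate or success rule, and it does not deserve high priority.

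Much of that stands. The intent is clear, wrongful exclusion is unlikely in practice, and the statistics are untouched. The omission of the annulus limit from the CIP Summary is not a second contradiction, because the summary lists key criteria only and points to the full list. The count of 30 to 60 depends on assumptions. In particular, the regional protocol is described as having aligned criteria but cannot be seen, so whether it repeats criterion 29 is unknown.

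What does not stand is the idea that evident intent settles the matter. Criterion 29 is an operative rule, Section 5.3.1 makes any exclusion decisive, and Section 10.7 grants no waivers. The likelier it is that sites follow the intent, the more enrolments run against the written protocol.

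**Conclusion.** The contradiction holds as stated. Under the current text, every Titan candidate above 27 mm meets an exclusion criterion, and only a measurement of exactly 27 mm satisfies both rules. About 30 to 60 Titan analysis subjects would be affected, assuming all measure above 27 mm and depending on how many enrol under this protocol; any Titan roll-ins come on top.

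The consequence is operational and regulatory: screen failures, or deviations that cannot be waived. It must be corrected because the rule as written bars nearly the whole target range of a cohort meant to support a marketing application.

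**What to change.** Issue a short protocol amendment that gives criterion 29 an explicit cohort scope and reconciles it with the cohort-specific ranges in Section 5.3.2.2, the any-exclusion rule in Section 5.3.1 and the CIP Summary in Appendix XXI. Which annulus limit governs each cohort is the sponsor's decision.

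In the same amendment, the sponsor should confirm how a subject at exactly 27 mm, who fits both inclusion ranges, is assigned to a cohort. Both ranges refer to the instructions for use, which may already settle this but are not among the documents reviewed.

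The cost is one amendment through the usual ethics and regulatory route. Sample size, analysis populations and endpoints are unaffected.

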## Clinical Investigation Plan

### 5.4 Subject Enrollment

The point of a subject's enrollment in the clinical study is completion of signing the informed consent.

Consented subjects who undergo study-specific testing and are found to have met exclusion criteria or not all inclusion criteria (or if a site disagrees with the Subject Selection Committee's decision regarding risk classification) will be considered screen failures; these subjects will not be counted toward the sample size of 169 analysis subjects and will be exited from the study without further follow-up.

In addition, consented subjects who undergo study-specific testing and meet study criteria but do not undergo a Navitor implant attempt (defined as insertion of the delivery system into the vasculature) will not be counted toward the sample size of 169 analysis subjects and will be exited from the study without further follow up.

All subjects who undergo a Navitor implant attempt will be included in the analysis population or designated as roll-in as described in Section 5.4.1. Subjects who undergo a Navitor implant attempt but are not implanted with the Navitor Valve will be followed for 30 days and then exited from the study; similarly, any subject who undergoes explant of the Navitor Valve during the study follow-up period will be exited from the study 30 days following the explant procedure.

#### 5.4.1 Roll-in Cohort

The requirement for roll-in cases will be determined based on experience of the implanting physicians. If neither of the implanting physicians have previous Portico with FlexNav clinical experience, a minimum of one roll-in subject will be required. Data from roll-in subjects will be analyzed separately as the "roll-in arm" and will not be included in the analysis population. A maximum of 20 roll-in subjects will be permitted in the study. Designation of roll-in or analysis subject will be made by the Sponsor in advance of the procedure. The combined Portico NG and Titan cohorts will not exceed a total of 20 roll-in subjects.

The total number of roll-in subjects required per site will be at the discretion of the Sponsor and will be based on the primary implanting physician's recent Portico implant experience.

#### 5.4.2 Enrollment of Medicare Beneficiaries

This clinical study will enroll subjects with Medicare benefits and therefore conforms to all standards of Medicare coverage requirements. The Risks and Benefits section describes how all enrolled subjects, including Medicare beneficiaries, may be affected by the device under investigation.

Subjects enrolled in the clinical study are expected to be consistent with the Medicare population based on age and as such, the clinical study results are expected to be generalizable to the Medicare population.

#### 5.4.3 Historically Under-Represented Demographic Subgroups

The Sponsor intends to ensure adequate representation of women and other traditionally under-represented demographic subgroups in this clinical study. Some barriers to participation of women and ethnic minorities in clinical studies have traditionally been:

- Lack of understanding about main obstacles to participation of such subgroups in clinical research
- Inclusion/exclusion criteria potentially not needed to define the clinical study population may unintentionally exclude specific subgroups
- Under diagnosis of disease etiologies and pathophysiology leading to lower referral rates of demographic subgroups

## Clinical Investigation Plan

- Avoidance of specific subgroups by investigators and Sponsors due to the perception that it takes more time and resources to recruit them
- Family responsibilities limiting women's ability to commit time for follow-up requirements

Historically, TAVR clinical studies performed in a similar patient population have shown the treatment population to be approximately 50% or higher female. Furthermore, the traditional barriers to enrollment of women (such as fear of fetal consequences, family responsibilities that may limit the ability for time commitment to trial follow-up) are not applicable in this study due to the expected average age of the patient population (> 80 years). Additionally, aortic stenosis is prevalent in traditionally underrepresented non-white subgroups based on data collected from over 18.9 million patients treated in the U.S. from 2002 to 2012 (74.8% White, 12.6% Black, 7.3% Hispanic, 1.9% Asian or Pacific Islander, 0.6% Native American, 2.8% other ethnicity).

In the Portico IDE randomized cohort, which enrolled subjects at sites in the United States and Australia, the study population was approximately 50% female and nearly 8% of non-white ethnicity. As the Portico NG study will also enroll subjects in the U.S., which has a diverse population, the proportion of females and the proportion of non-white subjects are expected to be comparable to that enrolled in the Portico IDE which had nearly identical inclusion/exclusion criteria. Therefore, there is no expected impact of the inclusion/exclusion criteria on the enrollment of females and ethnic minorities for the Portico NG study; specifically, the anatomical parameters required and devices sizes available allow for inclusion of female subjects and ethnicities with smaller anatomical measurements (i.e., small annulus diameters), and medical exclusion criteria are translatable to a general TAVR patient population deemed high or extreme risk for surgical valve replacement without any gender or racial bias. For the Titan cohort, the same principles apply, with the exception that due to the large annulus use range, it is anticipated there will be a larger proportion of male subjects as observed in clinical studies for FDA approved large valve devices (i.e., Evolut R 34mm).

The Sponsor will take the following steps to ensure adequate representation of women and racial or ethnic minorities in this clinical study:

- The Sponsor will provide training to investigational site personnel to ensure adequate representation of these demographic subgroups
- The Sponsor will regularly review enrollment data to investigate whether there is under-representation of these demographic subgroups
- The Sponsor will regularly review withdrawal rates for under-represented subgroups and compare these rates with that in the overall clinical study population
- As appropriate and necessary, the Sponsor will retrain sites on the importance of recruiting and retaining subjects in the clinical study
- The Sponsor will approach sites without bias or consideration for specific demographic subgroups

---

 Beydoun HA, Beydoun MA, Liung H, et al. Sex, Race, and Socioeconomic Disparities in Patients With Aortic Stenosis (from a Nationwide Inpatient Sample). *Am J Cardiol* 118 (6): 860-865.

## Clinical Investigation Plan

- The Sponsor will have informed consent materials in alternative languages and will work with sites and IRBs/ECs on recruitment materials

### 5.5 Subject Withdrawal

Each enrolled subject shall remain in the clinical study until completion of the required follow-up period; however, a subject's participation in any clinical study is voluntary and the subject has the right to withdraw at any time without penalty or loss of benefit. Conceivable reasons for discontinuation may include, but not be limited to, the following:

- Subject death
- Subject voluntary withdrawal
- Subject lost-to follow-up as described below
- Subject's follow-up is terminated according to Section 3.3.

The Sponsor must be notified by the site of subject's discontinuation as well as the reason(s) for subject discontinuation. Investigators must also report subject discontinuations to their respective IRB/EC as defined by their institution's procedure(s).

No additional follow-up will be required or data recorded from subjects once withdrawn from the clinical study. However, if a subject withdraws from the study due to problems related to the safety or performance of the device under investigation, the investigator shall ask for the subject's permission to follow his/her status/condition outside of the clinical study.

